 - c) greater improvement or lesser impairment of quality of life after reconstruction of floor of lesser pelvis
2. To study if the different rehabilitation programmes used reflect differences in outcome measures in subgroup analyzes for both methods of reconstruction
3. To compare the health economic costs with the two techniques and to perform a cost-utility analysis (QALYs gained). The health economic analysis is optional to participating centres. Costs and health economics will be calculated only in centres that have routine registration (in electronic databases) of operation time, time at ICU, days in hospital, connected reoperations, connected readmissions and outpatient visits related to the index operation.

Investigational plan

Endpoints of study

1. Primary endpoint: Performance in Timed-stands test (TST)[9, 10]reflecting physical performance at 6 months from operation.
2. Secondary endpoints:
 1. Change in physical performance (3 months, 6 months and 1 year compared to preoperative)
 2. Primary wound healing assessed with the Southampton Wound Assessment Scale (SWAS)[11] at 3 months from operation
 3. Complications according to classification by Dindo-Clavien[12] (3 months, 6 months and 1 year)
 4. Proportion of persistent perineal sinus or fistula (3 months, 6 months, 1 year)
 5. Ability to sit (3 months, 6 months, 1 year)
 6. Change of pain and discomfort in gluteal region measured with VAS (3 months, 6 months and 1 year compared to preoperative)
 7. Change of quality of life measured with EQ-5D and EORTC forms C30 and CR29 (3 months, 6 months and 1 year compared to preoperative)
 8. Quality of life spot measures at 3 months, 6 months and 1 year

9. Length of hospital stay, costs of surgical treatments and QALYs gained at one year
10. Local recurrence during study period

Hypotheses of study

Primary hypothesis:

1. The reconstruction of lesser pelvis floor with APCI will result in better physical performance in operated patients compared to patients operated on with GMF.

Secondary hypotheses:

1. The assumed decrease of physical performance after the APCI operation will be less than after the GMF operation.
2. The reconstruction of lesser pelvis floor with APCI will result in better wound healing and less wound complications than the GMF operation.
3. The reconstruction of lesser pelvis floor with APCI will result in better ability to sit and lesser pain and discomfort in the gluteal region than the GMF operation,

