We consider that a minimally important clinical effect applies for this study if results differ less than 10%. The noninferiority margin is thus set to 10%. This means that the results from study arms are considered clinically having no important differences if the results from test operation (APCI) differ less than 10% in the main outcome. We claim noninferiority for test operation if the result will be in the range less than 10% inferior result up to a trend for superior result but not statistically significant for the main outcome. If the result shows a statistically significant difference we claim superiority (or inferiority) of the test operation. If we find noninferiority based on the main outcome we may still draw conclusions about which operation should be preferred, based on results from secondary outcomes.

Data to be analyzed

All primary analyses in this study will be performed according to the intent-to-treat (ITT) principle, that is, patients will be allocated to treatment groups corresponding to their assigned treatment, even if the patient does not receive the correct treatment.

The intention-to-treat population will consist of all randomised patients who are operated with EAPE.

Per-protocol analyses are secondary and may be used if special circumstances motivate to use such. If noninferiority is to be stated we will do a per-protocol analysis in addition to the ITT analysis and if both analyses are non significant it will give more evidence of noninferiority. The per-protocol population will consist of all patients in the intent-to-treat population who have met all protocol requirements and who have successfully completed the trial up till one year.

Patient disposition

Reasons for discontinuations in the study will be compared between the 2 treatment groups. Result tables or the Consort[24] diagram will reveal the number and proportion of patients who have completed the study as well as patients that have discontinued, grouped by reason for discontinuation.

Patient characteristics

Age, gender, primary or recurrent rectal cancer will be registered when the patient is randomised via the web application and will be included in the summary reports.

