Preoperative oncologic treatment and pre- and postoperative tumour classification (cTNM and pTNM) will be registered in (and retrieved from) the Swedish Colorectal Cancer Registry for Swedish patients and for patients outside Sweden a similar form with TNM data is completed via the study homepage web application by the local investigator. The pTNM classification will also be included in the summary reports.

Primary analysis

Performance in Timed-stands test (TST) measured in seconds (time) will be compared between study arms at 6 months from the operation and tested with appropriate statistical tests. The proportion of patients that perform worse than the upper limit of reference values may be used as a parameter for comparison. TST reflects physical performance that is the primary outcome of the study.

Secondary analyses

1. The change of physical performance, i.e. the difference between preoperative and postoperative results in TST at 3, 6 and 12 months will be compared between study arms.
2. Primary wound healing at 3 months is categorized in subclasses (SWAS[11]) and the proportions of patients in different classes are compared between study arms.
3. Complications are categorized according to classification by Dindo-Clavien [12] and the proportions of patients in different classes are compared between study arms at 3, 6 and 12 months.

4. Ability to sit is defined in three classes and the proportions of patients in different classes are compared between study arms at 3, 6 and 12 months.
5. Pain and discomfort in gluteal region measured with VAS and analyzed with appropriate statistical methods. Comparisons will be done at 3, 6 and 12 months.
6. Quality of life is measured with EQ-5D and EORTC forms C30 and CR29 and the individual responses are calculated to a health utility index using an appropriate table/tariff for the general population[25, 26] Spot measures at 3, 6 and 12 months and differences between pre-treatment and postoperative measurements will be compared.
7. The proportion of patients that present local recurrence during the study period will be compared between study arms.

Subgroup analyses

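### The only per-protocol set requires one-year completion but supports a noninferiority statement on a 6-month outcome, so valid primary results are dropped for later events

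*Protocol*

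**What the plan says.** All places are in the protocol.

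- **Endpoints of study:** the primary endpoint is TST performance "reflecting physical performance at 6 months from operation".
- **Primary analysis:** TST in seconds "will be compared between study arms at 6 months from the operation and tested with appropriate statistical tests".
- **Interpretation of noninferiority:** the claim is assessed on the main outcome, with a margin of 10%. It covers results from less than 10% inferior "up to a trend for superior result but not statistically significant for the main outcome".
- **Data to be analyzed:** primary analyses follow ITT. On the other set: "Per-protocol analyses are secondary and may be used if special circumstances motivate to use such". For noninferiority the plan is firmer: "If noninferiority is to be stated we will do a per-protocol analysis in addition to the ITT analysis". The weight that agreement between the two would carry is put this way: "if both analyses are non significant it will give more evidence of noninferiority".
- **Data to be analyzed, definition of the set:** "all patients in the intent-to-treat population who have met all protocol requirements and who have successfully completed the trial up till one year". No other per-protocol set is defined, and none is tied to month 6.
- **Discontinuations:** results from patients who die or are lost to follow-up may be used up to the date of discontinuation. Patients who withdraw choose whether their data up to then are kept or erased.

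**The concern.** A per-protocol set should reflect whether a patient was treated and assessed as planned up to the time of the outcome. Here, membership for a 6-month outcome depends on what happens in the following six months. Take a patient who was eligible, received the allocated operation, was tested at 6 months and died at month 8. Nothing went wrong with the primary result, and the rules on discontinuation call it usable, yet the definition removes it.

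These are patients with primary or recurrent rectal cancer, and the sample size section allows for mortality, so some late loss is to be expected. If function at 6 months is related to later death or dropout, and the relation or the loss rate differs between arms, the per-protocol comparison of 6-month TST is distorted. The set also becomes smaller. That matters because the plan reads non-significance in both analyses as added evidence of noninferiority, and a smaller set reaches non-significance more easily.

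**Working it through.** **1. Time points side by side.** The outcome, the primary analysis and the noninferiority statement are all at month 6. The condition for entering the per-protocol set runs to month 12. Adherence is already covered by the requirement to have met the protocol. For the 6-month outcome, the one-year clause therefore adds only selection on what happens between months 6 and 12.

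**2. The plan's own sample size.** Inputs (Sample size section): low performance 63% with GMF and 30% with APCI, alpha 0.05, power 90% (fallback 80%), loss 20%. Sidedness is not stated; two-sided is assumed. With unpooled variance:

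n per arm = (z for alpha + z for power)² × [0.63×0.37 + 0.30×0.70] / 0.33²

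- 90% power: (1.960 + 1.282)² × 0.4431 / 0.1089 = 42.8, so 43; 43/0.8 = 53.75, so 54 per arm and 108 in total.
- 80% power: (1.960 + 0.842)² × 0.4431 / 0.1089 = 31.9, so 32; 32/0.8 = 40 per arm and 80 in total.

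Both stated totals reproduce. The point does not depend on them; they supply the base for step 3.

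**3. How many valid outcomes could be dropped.** The 20% is not split by time, so there are two readings.

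*(a) All of the 20% falls by month 6, and late loss comes on top (assumed rates).* Patients with a 6-month TST: 108 × 0.8 = 86.4, or 80 × 0.8 = 64 in the fallback. Power is for 63% versus 30% with the formula above. Half-width is that of the 95% interval for a difference with 63% in both arms, 1.96 × √(2×0.63×0.37/n).

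| Further loss, months 6-12 | Dropped of 86 | Left | Power | Half-width | Dropped of 64 |
|---|---|---|---|---|---|
| 0% | 0 | 86 | 0.90 | 20.4 points | 0 |
| 5% | 4 | 82 | 0.89 | 20.9 points | 3 |
| 10% | 9 | 78 | 0.87 | 21.5 points | 6 |
| 20% | 17 | 69 | 0.83 | 22.8 points | 13 |

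*(b) The 20% runs to month 12.* About 86 patients then complete one year, which is the planned evaluable number, and more than 86 have a 6-month TST. The number dropped is whatever part of the 108 × 0.2 = 21.6 losses falls after month 6.

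**4. Direction of bias (illustration only).** Assume true low-performance rates of 73% with APCI and 63% with GMF, a 10-point deficit, and read the margin as percentage points. Let 5% of everyone else be lost late and a fraction L of the low performers in one arm. The rate p in that arm becomes p(1−L) / [p(1−L) + (1−p)×0.95]; the other arm is unchanged.

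- Extra loss among APCI low performers, L = 20%: 0.584 / (0.584 + 0.2565) = 69.5%, and the difference shrinks to 6.5 points. With L = 10% and 30% it is 8.9 and 3.6 points.
- Extra loss among GMF low performers, L = 20%: 0.504 / (0.504 + 0.3515) = 58.9%, and the difference grows to 73 − 58.9 = 14.1 points.

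The same rule can move the result inside the margin or further outside it.

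**The case against.** The strongest defence is that the per-protocol analysis is secondary. ITT is primary, and agreement between the two only adds evidence. A patient operated with EAPE who has a 6-month TST is not removed from the ITT analysis by this clause. That stands. A reader might infer that the clause undermines the primary result or acts as a formal gate for noninferiority; the text supports neither.

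A reader might also infer that the clause favours noninferiority by trimming slow patients. The documents give no late loss by arm or by function, and step 4 shows that either direction is possible. A shift of about 0.15 SD can be obtained (0.195 − 0.049 SD for a normal outcome), but only if exactly the slowest 10% in one arm and the slowest 2% in the other are lost. That is an extreme case with nothing in the protocol behind it. Nor can a further 5-10% loss from a base of 86 be placed within the planned 20%, since that base has already used up the whole 20%.

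It can further be said that the 12-month visit is a scheduled examination, that one completer set for the 3-, 6- and 12-month endpoints is simple, and that excluding patients with expected survival under one year lowers late mortality. These points reduce the weight. They do not explain why a 6-month result should be discarded for a later event, and the survival criterion does not remove late deaths. Where a withdrawing patient asks for erasure, the data are lost to every analysis, and that is not due to this clause.

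**Conclusion.** Wrong as written, and minor, because it concerns a supportive analysis. The mismatch between a 6-month outcome and a one-year membership rule is certain from the text, and it conflicts with the protocol's own allowance to use data up to discontinuation. The consequence is a smaller set, selected on events after the outcome and open to bias of unknown sign, in the analysis meant to add weight to a noninferiority statement.

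The size cannot be determined from the documents. If 5-10% are lost after month 6 in addition to the planned 20%, about 4-9 of 86 valid outcomes go (3-6 of 64 in the fallback), with a modest loss of precision. The sample size and the ITT primary analysis need no change.

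**What to change.** For the 6-month primary endpoint, define the per-protocol set as ITT patients who were eligible, received the allocated reconstruction, met the protocol requirements up to the 6-month visit and had the 6-month TST assessed. Keep the one-year completion condition only for the 12-month endpoints.

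This costs one sentence under Data to be analyzed. It needs no extra visits, data or patients.

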The participants are examined by a physiotherapist or a study nurse who is familiar with the protocol. Examinations of physical performance, wound healing and registration of quality of life and background information takes place:

1. within one week before the start of radiotherapy (or operation if examination before RT can not be accomplished) (wound healing excluded)
2. three months after the operation
3. six months after the operation
4. one year after the operation
5. at one late time point 2-5 years after the operation if previous analyses indicates a need for long time follow-up. The long time follow-up is optional for participating centres and will be decided later.

A separate detailed protocol of standardized examination procedures will be available for the physiotherapists and nurses involved in the study. A pre-study meeting for standardization of examinations will be arranged for participating centres.

The standardisation of operations will be secured with site visits from (or to) Stockholm Karolinska Sjukhuset Solna where the standard for GMF and APCI operations is defined.

The enrolment of a patient in the study is finalized with the randomization procedure on Internet. The web application at www.norrlandskirurgi.se is used for randomization.

The randomization is computed in blocks and stratified by:

- Centre
- Mode of preoperative radiotherapy (RT)
 - Short preoperative RT, (5 x 5 GY), **operation within one week from last RT dose**
 - Short preoperative RT, (5 x 5 GY) or long preoperative RT (25 x 1,8/2 GY), **operation 4 - 8 weeks from last RT dose**
 - Earlier RT for organs in the lesser pelvis in connection to a previous therapy but no additional RT before the current operation or other RT dose or timing of operation

The stratification and block randomization ensures that all above defined subgroups of patients will contain patients allocated evenly (or close to evenly) to both study arms. The size of the randomisation blocks will vary within predefined limits and the size of the block under use will be chosen by random from the alternatives given of limits.

Flowchart of NEAPE study

Surgeon and study nurse

MDT conference

- Identify APE and EAPE candidate patients =eligible rectal cancer patients
- Study nurse enter identified patients in register at www.norrlandskirurgi.se

Study nurse

For EAPE candidates, send invitation for preoperative visit to surgeon and physiotherapist or study nurse

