- Inform physiotherapist and book the visit
- Include patient information of NEAPE study with invitation to patient
- Include preoperative quality of life forms
- Include information of routine registration in study register and CRC register

Enrol

Surgeon

Preoperative visit to attending surgeon

- Check for eligibility
- Inform patient of NEAPE study
- Get informed consent if conditions met and file the document
- Randomise/Enrol if decision of standard EAPE can be made

Physiotherapist or study nurse

Preoperative visit to physiotherapist (before RT if possible)

- Fill preoperative form (P1)
- Check and collect QoL forms and inform patient if necessary for complete data
- Perform physical tests and register results on form (P2)
- Register all collected data into the electronic database on Internet

Surgeon

Operation

- Check for eligibility
- Operate according to allocation and NEAPE study standard
- Randomise/Enrol if decision of standard EAPE can be made only at this point
- Follow NEAPE perioperative standards

Study nurse Weekly check-up that all patients operated on with APE or EAPE at the hospital are either randomised or registered and that correct/completed registration data is saved

- This will be the final data for non-randomised patients

Follow-up

Study nurse Send invitation for postoperative visit at 30 days

- Include postoperative quality of life forms

Surgeon

30 days postoperative NEAPE follow-up visit to attending surgeon

- Fill form of staging and TNM classification (form S1)
- Check for early complications and register on form (S2)
- Classify wound healing and all complications on form (S3)

Study nurse Send invitation for postoperative visit at 3 months

- Include postoperative quality of life forms

Surgeon

3 months postoperative NEAPE follow-up visit to attending surgeon

- Check for late complications and register on form (S4)
- Classify wound healing and all complications on form (S3)

Physiotherapist or study nurse

3 months postoperative NEAPE follow-up visit to physiotherapist

- Check and collect QoL forms and inform patient if necessary for complete data
- Perform physical tests and register results on form (P2)
- Fill postoperative form (P3)
- Register all collected data into the electronic database on Internet

Study nurse Send invitation for postoperative visit at 6 months

- Include postoperative quality of life forms

Surgeon

6 months postoperative NEAPE follow-up visit to attending surgeon

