Once per year an independent advisor that together with the PI has the authority to stop the study if serious unexpected safety issues can be observed will evaluate the collected data of clinical adverse events. If the independent advisor and the PI make a decision to stop the study, the decision must be written and motivated in detail and distributed to all participating centres without delay.

Quality control and quality assurance

To ensure accurate and reliable data the study administration will do the following:

- Provide instructional material to the study sites, as appropriate (manual for physical examination etc.)
- Update study homepage at www.norrandskirurgi.se with relevant information and study material
- Start-up training, meeting with investigators
- Be available for consultation
- Conduct quality review of database (a monitor may be sent to participating centres)

Data analysis methods

Sample size

The sample size is calculated with the following assumptions:

- Estimated proportion of patients with low performance in TST with GMF 63%
- Estimated proportion of patients with low performance in TST with APCI 30%
- Estimated loss of data/cases 20% (mortality etc.)

The calculation gives that a total of 108 patients (54 patients in each study arm) are needed with 90% power and a significance level of 0.05 (alpha).

If the anticipated three-year inclusion phase of the study is too short for including 108 patients an alternative power calculation with 80% power will be used instead and the study will include a total of 80 patients only before the inclusion phase will be closed.

Interpretation of noninferiority

The noninferiority margin for the study is set on the basis of a minimally important clinical effect, which is a subjective judgement of the best expertise available. This approach remains the only alternative since there are no historical placebo controlled trials in the field for guidance and for practical reasons such trials are not possible to conduct.

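### Nothing requires the preoperative TST and pain baseline to precede open randomisation, and the only stated use of the preoperative TST is a raw change score

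*Protocol*

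**What the plan says.** The primary endpoint (Protocol, Endpoints of study) is a value at one time point, not a change: "Performance in Timed-stands test (TST)[9, 10]reflecting physical performance at 6 months from operation". Under Primary analysis, TST in seconds "will be compared between study arms at 6 months from the operation and tested with appropriate statistical tests", with a binary alternative: "The proportion of patients that perform worse than the upper limit of reference values may be used as a parameter for comparison". No test or covariate is named.

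The preoperative TST appears in one analysis, the first under Secondary analyses: "the difference between preoperative and postoperative results in TST at 3, 6 and 12 months will be compared between study arms". Endpoints of study also lists change from the preoperative value for pain and discomfort (VAS) and for quality of life.

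On allocation, Summary of study design says "The randomization is computed in blocks and stratified by" centre and three radiotherapy categories. The same section ties the baseline examination to the week before radiotherapy, or before the operation if that is not feasible. It does not tie it to randomisation. In the Flowchart of NEAPE study, the surgeon's preoperative visit includes randomisation when the operation can already be decided. The next entry is "Preoperative visit to physiotherapist (before RT if possible"), with the preoperative form, the physical tests and the collection of QoL forms. Recommended procedure also has the surgeon randomise at the preoperative examination. Recommended procedure and Patient assignment both allow intra-operative randomisation when eligibility is uncertain. Blinding states that surgeon, examiner and patient need not be blinded.

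**The concern.** A baseline is safe as a reference or a covariate only if allocation cannot influence it. Chair-rise time depends on effort and on how the examiner conducts the test, and pain is self-reported. If patient and examiner already know the arm, expectation can shift the baseline differently in the two groups. That shift passes directly into every change-from-baseline comparison, and no later analysis can remove it.

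The second issue is efficiency. A raw change score subtracts the whole baseline whatever its correlation with the outcome. When the correlation is modest, this adds noise. The trial expects about 86 evaluable patients, or 64 under the fallback, and it already collects a better use of the same measurement.

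**Working it through.** **Order of baseline and allocation.** No arithmetic applies, so the sections are set side by side.

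- Flowchart of NEAPE study: randomisation at the surgeon's preoperative visit is listed first and the physiotherapist's tests after it.
- Summary of study design: baseline timing is linked to radiotherapy or operation only.
- Blinding: examiner and patient are open.
- No section requires the baseline tests to come before randomisation.
- Intra-operative randomisation: the baseline necessarily comes first.
- QoL: the forms go out with the invitation, before the surgeon's visit, and the physiotherapist only checks and collects them. They are less exposed than TST and pain.

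The exposure is therefore limited to patients randomised preoperatively, and within them mainly to the TST and VAS change endpoints. The documents give no basis for putting a number on the bias.

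**The plan's sample size.** Inputs from Sample size: "Estimated proportion of patients with low performance in TST with GMF 63" per cent; "Estimated proportion of patients with low performance in TST with APCI 30" per cent; 20% loss; alpha 0.05, taken as two-sided. The unpooled two-proportion formula is

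n per arm = (1.960 + z)² × (0.63×0.37 + 0.30×0.70) / 0.33²

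- 90% power: 42.75, rounded up to 43; 43/0.8 = 53.75, rounded up to 54 per arm, 108 in total.
- 80% power: 31.94, rounded up to 32; 32/0.8 = 40 per arm, 80 in total.

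Both stated totals reproduce. Evaluable patients per arm are 54×0.8 = 43.2 and 40×0.8 = 32.

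**Variance factors on the seconds scale**, relative to an unadjusted 6-month comparison, with equal variance before and after operation and correlation r:

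- ANCOVA: 1 − r²
- raw change: 2 − 2r
- difference: (2 − 2r) − (1 − r²) = (1 − r)², which is never negative. The change score is therefore never better than ANCOVA, and 2 − 2r exceeds 1 when r < 0.5.

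**Power**, anchored so that the unadjusted analysis has exactly the planned power at the evaluable n (normal approximation; standardised effects 0.697 and 0.700). The values of r are assumptions.

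| r | ANCOVA factor | Change factor | 108 randomised: ANCOVA / change | 80 randomised: ANCOVA / change |
|---|---|---|---|---|
| 0.3 | 0.91 | 1.40 | 92.5% / 78.2% | 83.6% / 65.8% |
| 0.5 | 0.75 | 1.00 | 96.3% / 90.0% | 89.9% / 80.0% |
| 0.7 | 0.51 | 0.60 | 99.5% / 98.7% | 97.5% / 95.1% |

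At r = 0, ANCOVA gains nothing.

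**Sensitivity to the effect size.** If TST were normal with equal SDs, 63% against 30% would imply a difference of z(0.63) − z(0.30) = 0.86 SD. Unadjusted power on seconds would then already be 97.8% (43.2 per arm) and 92.9% (32 per arm). ANCOVA would raise these to 98.7% and 94.8% at r = 0.3, and to above 99.5% for both at r = 0.7.

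**The case against.** The strongest reply is that the choice of model and covariates commonly belongs in the SAP, which is not at hand, and that the wording of the primary analysis leaves room for adjustment. That stands. A reader might infer that the primary analysis ignores the baseline and the strata. The document does not support this: it is silent, and silence here is not an error. A 6-month value as primary endpoint with change as secondary is also a legitimate choice.

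A reader might also infer a large loss of power, for example by assuming an effect of 0.5 SD and r of at least 0.5. Neither figure is in the documents. The planned proportions point to a larger standardised effect, under which the absolute gain is small. Radiotherapy, major surgery and six months may separate baseline and outcome, so a lower r is plausible. The factor 1 − r² also does not carry over directly to the binary parameter on which the trial was sized.

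Nor is adjustment free under the present order. If allocation can influence the baseline, adjusting the primary endpoint for it could bring bias into a comparison that is now immune to this problem.

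Finally, the flowchart lists steps by role, its layout is lost in the text, and both visits arise from one invitation, so it permits the unfavourable order without mandating it. This is true, but nothing excludes that order, and the protocol is the document that has to exclude it.

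**Conclusion.** The point holds in two limited parts.

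- **Timing of baseline.** For patients randomised preoperatively, the protocol allows TST and pain baselines to be recorded after an open allocation. The secondary change endpoints for TST and VAS could be biased, and QoL less so. The unadjusted 6-month TST and patients randomised intra-operatively are unaffected. The size cannot be estimated.
- **Use of baseline.** The one stated use of the preoperative TST is a raw difference, which is never more efficient than ANCOVA and is worse than no adjustment below r = 0.5. Adjusting the primary comparison is a recommended improvement, not the correction of an error. For r = 0.3 to 0.7 (assumed), it would turn 90% power into about 92.5% to 99.5%, and 80% into about 84% to 97.5%, on the seconds scale only. The absolute gain is smaller if the planned effect is near 0.86 SD.

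The second part depends on the first: adjustment is safe only once the baseline is fixed before allocation.

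**What to change.** 1. In the flowchart and Recommended procedure, require forms P1 and P2 (with the pain assessment) and the QoL forms to be completed before web randomisation is opened. Cost: randomisation may have to wait for the physiotherapist visit.
2. With that order fixed, replace raw change scores for TST, VAS and QoL at 3, 6 and 12 months with comparisons adjusted for the preoperative value (ANCOVA, or rank-ANCOVA if times are skewed). Cost: wording only.
3. In the protocol or SAP, specify the primary analysis as 6-month TST in seconds by arm, adjusted for preoperative TST and radiotherapy stratum. Enter centre as a random or pooled effect. With a minimum of 6 patients per centre there could be up to 108/6 = 18 centres, and 18 × 3 = 54 cells for 108 patients, too sparse for full stratum terms. Cost: wording, plus a stated rule for missing baselines.

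No change to the sample size is needed.

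### The sample size is set on the proportion of low performers, the primary analysis compares seconds with that proportion as an option, and nothing says which decides.

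*Protocol*

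**What the plan says.** Four places in the protocol bear on this.

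- **Endpoints of study** names the outcome without a scale: "Primary endpoint: Performance in Timed-stands test (TST"), at 6 months from operation.
- **Measures of physical performance** records the test as the time taken for ten stands, so the raw measurement is continuous.
- **Sample size** works only with a binary outcome: "Estimated proportion of patients with low performance in TST with GMF 63"% and "Estimated proportion of patients with low performance in TST with APCI 30"%, with "Estimated loss of data/cases 20% (mortality etc".). It concludes: "The calculation gives that a total of 108 patients (54 patients in each study arm) are needed with 90% power", at a significance level of 0.05. If three years of inclusion do not suffice, the target falls to 80 patients at 80% power.
- **Primary analysis** says that TST in seconds will be compared between arms at 6 months, with the test left open. It then adds: "The proportion of patients that perform worse than the upper limit of reference values may be used as a parameter for comparison".

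Interpretation of noninferiority rests the claims of superiority, inferiority and noninferiority on the main outcome, with a 10% margin whose scale is not given. Under Blinding, the protocol states that no blinding is attempted for surgeon, examiner or patient.

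**The concern.** The variable that carries the power calculation is not the variable that the primary analysis commits to. Seconds are the firm comparison, yet no target difference or SD in seconds appears anywhere. The proportion is only an option, yet the whole sample size rests on it.

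Two things are at stake. First, a reader who takes 90% (or 80%) as the power of the primary comparison is relying on a figure for a different analysis. Second, the option sits under Primary analysis with no condition for its use. If the two measures disagree, the protocol does not say which one settles the primary hypothesis. Everyone who produces or handles the outcome is unblinded, so an open choice has no other safeguard. The 10% margin has the same gap: ten per cent of a time in seconds and ten percentage points of low performers are different quantities.

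**Working it through.** **Inputs.** From Sample size: 63% and 30% low performers, 20% loss, alpha 0.05, power 90% or 80%, 54 or 40 patients per arm. Sidedness is not stated for the primary test; two-sided is assumed because it reproduces the figures.

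**1. Reproducing the stated size.** Two proportions, unpooled variance, normal approximation:

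n per arm = (z₀.₉₇₅ + z_power)² × [p₁(1−p₁) + p₂(1−p₂)] / (p₁−p₂)²

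- Variance term: 0.63×0.37 + 0.30×0.70 = 0.4431. Squared difference: 0.33² = 0.1089.
- 90% power: (1.960+1.282)² × 0.4431/0.1089 = 42.75. Divided by 0.8 this is 53.4, so 54 per arm, 108 in total.
- 80% power: (1.960+0.842)² × 0.4431/0.1089 = 31.94. Divided by 0.8 this is 39.9, so 40 per arm, 80 in total.

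Both totals match, which confirms that the stated power belongs to the proportion. The evaluable numbers after loss are 54×0.8 = 43.2, taken as 43, and 40×0.8 = 32 per arm.

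**2. Power of the proportion at those numbers.** Summing exact binomial probabilities over all tables that an uncorrected chi-square test rejects at two-sided 0.05 gives 87.5% at 43 per arm and 79.3% at 32 per arm. The unpooled formula is slightly optimistic.

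**3. Power of the comparison in seconds.** The protocol gives no mean difference and no SD, so the standardised difference has to be assumed. Two-sample t-test, two-sided 0.05:

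| Assumed difference | 43 per arm | 32 per arm |
|---|---|---|
| 0.4 SD | 45% | 35% |
| 0.5 SD | 63% | 50% |
| 0.6 SD | 79% | 66% |
| 0.7 SD | 89% | 79% |
| 0.8 SD | 96% | 88% |

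90% power at 43 per arm needs 0.71 SD; 80% power at 32 per arm also needs 0.71 SD.

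As an illustration only, suppose TST times are normal with a common SD and one cut-off for all patients. Then 63% against 30% is a shift of 0.332 − (−0.524) = 0.86 SD, and the power in seconds is 97.5% at 43 per arm and 92% at 32 per arm.

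**4. Type I error if either result may count.** Null trials were simulated with normal times, a t-test on the times, a chi-square test on the dichotomy, and a low-performer rate of 30%, 46.5% or 63% in both arms. With 43 per arm, at least one test rejects at 0.05 in about 7.6% to 8.4% of trials. With 54 per arm the range is about 7.3% to 8.1%. In round terms that is 7.5% to 8.5%. Two independent tests would give 1 − 0.95² = 9.75%; the correlation between the measures keeps the figure below that.

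**The case against.** The sentence on the proportion can be read as describing a supplementary analysis: seconds are what will be compared, and the proportion is permitted alongside. A statistical analysis plan, not shown here, may have settled the matter before any data were seen. Not naming the test is ordinary in a protocol and is no fault, so inflation from a free choice among tests on seconds should not be counted; the figures above do not count it. This stands, and it limits the type I error to what the wording allows. It does not remove the point. The sentence is placed under Primary analysis, not Secondary analyses, and the proportion is the only basis for the sample size, so it cannot simply be taken as supplementary. Nor would a later plan make the power paragraph describe seconds.

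A reader might infer that the trial is underpowered for seconds. The documents do not support that. A continuous comparison often has more power than its dichotomised version, and under the illustrative normal shift it exceeds the stated figures even at the smaller size. That illustration is not evidence of adequate power either, since the protocol states none of its assumptions.

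A reader might also infer that the measure was, or will be, picked after inspecting results. The text leaves room for it but does not show it.

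Finally, one could hold that only seconds will do, because dichotomising loses information. That goes too far. A patient who cannot complete ten stands has no time in seconds but can be classed as a low performer, and the protocol's ability-to-sit categories foresee patients unable to sit at all. Nor does anything in the protocol support a log scale.

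**Conclusion.** The point holds. The 90% and 80% power statements describe the comparison of proportions, while the comparison that the protocol commits to is in seconds, with power that cannot be derived from it: about 45% to 96% at 43 evaluable per arm for assumed differences of 0.4 to 0.8 SD. If both measures remain eligible to decide, the false-positive rate is about 7.5% to 8.5% instead of 5%, assuming roughly normal times and one test per measure. This is a mismatch and an open choice in the wording, not a demonstrated shortage of patients and not proof of selective analysis. It should be corrected because the primary decision, its error rate and the scale of the margin all depend on it.

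**What to change.** Name one deciding primary variable at 6 months, label the other as supportive, delete the sentence that makes the proportion optional, and state the power and the 10% margin on the chosen variable's scale. Two routes are equally acceptable.

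- **(a) Seconds.** State that 43 evaluable patients per arm give 90% power for a difference of about 0.71 SD, and that 32 per arm give 80% power for the same difference. Do not present 0.71 SD as the translation of 63% against 30%; under the normal-shift assumption that translation is 0.86 SD. State how patients who cannot complete ten stands are scored.
- **(b) The proportion.** Keep 108 and 80 patients. Define low performance as worse than the upper reference limit. Restate power as about 87.5% at 43 and 79% at 32 evaluable per arm (chi-square).

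Either route changes wording only and needs no extra patients. The cost is giving up the freedom to switch measures.
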